# 8. Quality Assurance and Control

#### 8.1 Risk Assessment

A Risk assessment has been conducted which acknowledges the potential risks to the trial. This section provides an overview of the Quality Assurance (QA) and Quality Control (QC) measures that will be put in place to ensure the trial is performed and data generated and recorded in accordance with the principles of ICH GCP.

#### 8.2 Central Monitoring at CTU

The CTU data managers will review all data received for errors and missing data points.

#### 8.3 On-Site Monitoring

The frequency, type and intensity for routine monitoring and the requirements for "for cause" monitoring will be detailed in a separate monitoring plan.

#### 8.3.1 Direct access to patient records

Participating investigators should agree to allow trial-related monitoring, including audits, ethics committee review and regulatory inspections by providing direct access to source data and documents as required. Patient consent must be obtained for this.

#### 8.3.2 Confidentiality

The data will be handled in accordance with the principles of the UK Data Protection Act.

#### 9. Statistical Considerations

#### 9.1 Method of Randomisation

The randomisation process will consist of computer generated block randomisation. Patients will be allocated in a ratio of 1:1 and randomisation will be stratified by site.

#### 9.2 Outcome Measures

The occurrence of the primary outcomes and secondary outcomes will be ascertained after analysis from the data sourced from local electronic blood transfusion registers, laboratory value database, and medical records systems. Patient self-reported quality of life will be obtained using the EuroQoL/ EORTC QLQ C30 forms tools at the start of the study and end of cycles.

#### 9.2.1 Primary Outcomes

**Adherence:** The percentage of pre-transfusion haemoglobin concentrations being below the target range of the assigned red cell transfusion strategy will be summarised for each treatment strategy

Haemoglobin difference: Achievement of at least a 15g/L difference between the mean pre-transfusion haemoglobins in the two treatment arms. This comparison will be done for each study day as well as overall.

#### 9.2.2 Secondary Outcomes

Overall haemoglobin difference: mean haemoglobin for the liberal and restrictive strategies using all haemoglobins reported.

**Adherence:** These will be measured by determining:

- The proportion of enrolled participants for whom the transfusion policy was successfully followed until the end of that chemotherapy cycle/death, whichever comes first. The transfusion policy will be defined as having been successfully followed if the participant always received a RBC transfusion within the defined time frame when their haemoglobin dropped below the trigger level, and did not receive any RBC transfusions when their haemoglobin was above the trigger level.
- The proportion of enrolled participants for whom the transfusion policy was successfully followed but allowing for one 'violation'.
- The proportion of transfusions per participant that were correctly given according to their haemoglobin trigger (i.e. had a haemoglobin value ≤70 g/L in the restrictive transfusion group and a haemoglobin value ≤90 g/L in the liberal transfusion group).
- The proportion of times a participant received a transfusion contrary to their haemoglobin trigger (i.e. had a haemoglobin value >70 g/L in the restrictive transfusion group and a haemoglobin value >90 g/L in the liberal transfusion group).
- The overall proportion of transfusions that were correctly given according to the participant's haemoglobin trigger (i.e. had a haemoglobin value ≤70 g/L in the restrictive transfusion group and an haemoglobin value less than ≤90 g/L in the liberal transfusion group).
- The overall proportion of times a transfusion was given contrary to the participant's haemoglobin trigger (i.e. had a haemoglobin value >70 g/L in the restrictive transfusion group and an haemoglobin value >90 g/L in the liberal transfusion group).

- The overall proportion of transfusions that were given correctly according to the participant's haemoglobin trigger by whether given as inpatient or outpatient
- The proportion of inpatient and outpatient transfusions given as single or multiple unit transfusions
- Percentages of transfusions performed where the pre-transfusion haemoglobin concentrations fell below, within and above the target haemoglobin range
- Percentages of transfusions performed where the post-transfusion haemoglobin concentrations fell below, within and above the target haemoglobin range
- **Recruitment rate:** the proportion of eligible participants enrolled will be summarised, along with the number of replaced participants and participant tolerability by transfusion strategy **and reasons for withdrawing early from the study.**
- Red Blood Cell Exposure: The difference in number of red blood cell units administered will be compared between the intervention groups up to death/end of chemotherapy cycle (whichever comes first).
- QoL questionnaire compliance: this will be summarised by treatment strategy and timepoint

Protocol adherence will be measured over time, to determine if adherence rates improve. Adherence rates will also be compared between transfusion arms and between sites. Transfusions will only be viewed as having successfully followed the transfusion policy if they are given within the pre-defined time period of 24 hours after a participant's haemoglobin has dropped below the trigger level. **Key** clinical characteristics of **recruited participants will be compared against** patients recruited to **the** AML 18 and 19 trials (in order to give a measure of patients excluded from this feasibility study which may be attributed to physician discretion).

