#### 5.7 Protocol Treatment Discontinuation

In consenting to the trial, participants are consenting to the trial treatment, trial follow up and data collection. However, a participant may stop treatment early or be stopped early for any of the following reasons:

- Participant moves to supportive care only prior to the end of the 2nd cycle
- Unacceptable adverse event
- Any change in the participant's condition that justifies the discontinuation of treatment in the opinion of the clinician
- Withdrawal of consent

Participants who undergo one cycle of chemotherapy and proceed straight to allogeneic stem cell transplantation will not be eligible to continue in the study following the first cycle of chemotherapy.

As the patient's participation in the trial is entirely voluntary they may choose to discontinue the trial treatment at any time without penalty or loss of benefits which they are otherwise entitled. Although the participant is not required to give a reason for discontinuing their trial treatment, a reasonable effort should be made to establish this reason while fully respecting the participant's rights.

Participants should remain in the trial for the purpose of follow up and data analysis, unless they withdraw their consent from all stages of the trial, in which case, they should be withdrawn. Data collected until the time of withdrawal will be retained and included in the analysis.

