#### 9.4 Analysis Plan (brief)

The analyses will be described in detail in a full Statistical Analysis Plan. This section summarises the main issues.

Appropriate statistical methods for the analysis of cross-over trials will be used. These may include mixed-effects models with a random effect for participant, paired methods or another suitable method, with adjustment for any period effect between cycles. The primary analysis will be performed according to intention to treat.

Data from all randomised participants who have received any transfusions will be included in the 'compliance to treatment threshold' analysis. Percentage compliance of pretransfusion haemoglobin concentrations being **below** the target range of the RBC transfusion threshold assigned will be presented by allocation arm. The percentage of pretransfusion haemoglobin concentrations falling below, within and above the target range will also be presented by allocation arm. The proportion of transfusions, proportion of participants and proportion of transfusions per participant given correctly, according to the algorithm, will also be calculated for each allocation arm.

The mean pre-transfusion haemoglobin level for each participant (regardless of whether they received a transfusion) will be calculated for each course of chemotherapy, then 2 overall means will be calculated for the restrictive and liberal groups, and the difference determined, looking for at least a 15g/L difference.

We will consider this study feasible and worthy of further development into a larger randomised trial if compliance for adherence is ≥70% in both arms. This will be reported by calculating the percentage of haemoglobin measurements that fall within or above their assigned target range pre- transfusion.

For analysis of other measures of feasibility, all patients who are eligible and ineligible will be documented and the proportion of randomised patients noted. Those who consented to and were enrolled in the trial will be analysed, even if they did not receive any transfusions, to understand reasons for failure to complete the assigned strategy.

Participants who completed QoL questionnaires will be included in the QoL analysis. The minimum required number for this analysis is completed QoL questionnaire at baseline, and after one chemotherapy cycle The percentage compliance with completing the QoL questionnaires will be summarised for each arm and each timepoint.

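### Participant-level adherence has two different denominators (all enrolled in 9.2.2, transfused participants only in 9.4), and the protocol does not say how participants without a second cycle are scored

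*Protocol*

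**What the plan says.** Protocol section 9.2.2 lists two adherence outcomes whose unit is the participant. The first is "The proportion of enrolled participants for whom the transfusion policy was successfully followed until the end of that chemotherapy cycle/death", whichever is earlier. The second is "The proportion of enrolled participants for whom the transfusion policy was successfully followed but allowing for one 'violation". Both take enrolled participants as the denominator.

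The same section defines success by two conditions. The policy was followed "if the participant always received a RBC transfusion within the defined time frame when their haemoglobin dropped below the trigger level", and the participant "did not receive any RBC transfusions when their haemoglobin was above the trigger level". Section 9.2.2 also plans to compare adherence rates between arms and between sites.

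The adherence paragraph of section 9.4 opens with a different set: "Data from all randomised participants who have received any transfusions will be included in the 'compliance to treatment threshold' analysis". Later in that paragraph it adds that the "proportion of participants and proportion of transfusions per participant given correctly, according to the algorithm, will also be calculated for each allocation arm". No other analysis set is named in the paragraph. Enrolled participants without any transfusion appear further down in 9.4, under other measures of feasibility, where the purpose is to understand why a strategy was not completed.

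Section 5.7 foresees participants who leave after cycle 1: "Participants who undergo one cycle of chemotherapy and proceed straight to allogeneic stem cell transplantation will not be eligible to continue in the study". It also lists a move to supportive care and withdrawal of consent. Sections 6.6 and 6.7 replace participants who discontinue their allocation in cycle 1 or are lost before cycle 2. None of these sections says how such participants are scored for the strategy they did not start.

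**The concern.** A proportion is defined only once its denominator is fixed, and here the protocol fixes two. An analyst following 9.2.2 and one following 9.4 could report different values for the same secondary outcome from the same data.

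The difference concerns the participants an adherence measure is meant to classify. Someone who met the trigger throughout a cycle and was never transfused is the clearest possible failure of the policy. Someone who never met the trigger and was not transfused followed it perfectly. Section 9.2.2 scores both, and the transfused-only set removes both. The removal need not be even between strategies. A haemoglobin that stays between 71 and 90 g/L meets the liberal trigger but not the restrictive one, so correct non-transfusion can occur more easily under the restrictive policy.

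The enrolled denominator has its own weakness. In a crossover where some participants have only one cycle, it includes people who were never exposed to the second strategy. Whichever way they are scored, that strategy's rate no longer describes adherence among those treated under it.

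**Working it through.** **The plan's own figures.** The protocol states no expected value for participant-level adherence, so there is no figure to reproduce on this outcome. The sample size in 9.3 does reproduce. The SD of the difference is 20 × √(2 × (1 − 0.25)) = 24.49 g/L, and a two-sided paired t-test at 0.05 for 15 g/L has power 0.910 with 31 patients. Then 31/0.9 = 34.4, which rounds up to 35 and then to the even number 36. Only the 36 and the 10% drop-out are used below.

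**Who is in each set, for one strategy**

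| Participant | 9.2.2 (enrolled) | 9.4 (transfused only) |
|---|---|---|
| Met trigger, never transfused | counted, failure | dropped |
| Never met trigger, not transfused | counted, success | dropped |
| Transfused at least once | counted, scored by rule | counted, scored by rule |
| Never started the cycle | counted, scoring not stated | depends on how 9.4 is read |

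The last cell is open because 9.4 does not say whether the transfusion must fall in that cycle or anywhere in the trial.

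**Step 1: enrolled versus transfused only.** Assume 36 participants under a strategy, all of whom start the cycle, with *k* never transfused. The protocol gives no value for *k*, so 2 and 4 are assumptions, as are the adherent counts.

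| *k* | Adherent among transfused | Transfused only | Enrolled, the *k* never met the trigger (successes) | Enrolled, the *k* were omissions (failures) |
|---|---|---|---|---|
| 2 | 27 of 34 | 27/34 = 79.4% | (27 + 2)/36 = 80.6% | 27/36 = 75.0% |
| 4 | 26 of 32 | 26/32 = 81.2% | (26 + 4)/36 = 83.3% | 26/36 = 72.2% |

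Moving from the 9.4 set to the 9.2.2 set changes the result by about +1 to −4 points with 2 untransfused, and by about +2 to −9 points with 4.

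**Step 2: participants who never start cycle 2.** The 10% drop-out in 9.3 gives 0.10 × 36 = 3.6, so take 4 non-starters, split evenly as 2 per strategy. Hold enrolment at 36 and set true adherence at 80% among those who started (both assumed).

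- Started the strategy: 36 − 2 = 34. Adherent: 0.80 × 34 = 27.2.
- Rate among starters: 27.2/34 = 80.0%.
- Enrolled denominator, non-starters as failures: 27.2/36 = 75.6%.
- Enrolled denominator, non-starters as successes because neither way of failing could occur: (27.2 + 2)/36 = 81.1%.

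The protocol gives no rate of transplant after cycle 1. As a range, 9 non-starters (4.5 per strategy) give 0.80 × 31.5 = 25.2 adherent, hence 25.2/36 = 70.0% as failures and (25.2 + 4.5)/36 = 82.5% as successes. The gap between the two scorings is about 5.6 points with 4 non-starters and 12.5 points with 9.

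**Step 3: does this reach the feasibility decision?** No. The 70% criterion in 9.4 is the percentage of pre-transfusion haemoglobin measurements within or above the target range. Its unit is the measurement, so the participant denominators above do not enter it. The primary adherence outcome in 9.2.1 is likewise built on pre-transfusion haemoglobins.

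**The case against.** **The 9.4 restriction may cover only the pre-transfusion haemoglobin measure.** The sentence after the restriction concerns that measure, which exists only where a transfusion was given, and the participant proportion comes later in the paragraph. This reading is possible. The text does not make the separation, however, and where 9.4 wants untransfused participants included it says so, for a different purpose. The contradiction stands as written, though it may be one of drafting rather than intent.

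**Few participants will be untransfused.** Section 1.1 reports an average of 11–12 red cell units in the first intensive course. This stands: the two sets should nearly coincide, and *k* = 4 is probably generous.

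**Details belong in the SAP.** How to score a participant without a second cycle is ordinary SAP content, and its absence alone would not be a finding. It matters here because the protocol itself fixes a denominator that includes these participants. Section 9.2.2 already reports replacements and reasons for early withdrawal, which covers part of what is needed.

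**A reader might infer that non-starters count as failures against the strategy they never received.** The protocol does not say so. Success is judged to the end of the cycle in question, which can be read as covering started cycles only. Under the two written conditions a non-starter has failed neither, so default success is at least as literal a reading. Only the absence of a rule is established.

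**A reader might also build a large spurious difference between strategies.** If all 4 non-starters fell in one sequence and were scored as failures, 70% true adherence would appear as 0.70 × 32/36 = 62.2% against 70.0%. That needs the unsupported failure reading and an extreme split. With 18 per sequence and losses at random, all 4 fall in one sequence with probability 2 × C(18,4)/C(36,4) = 6,120/58,905, about 10%. It also ignores the replacement rules in 6.6 and 6.7.

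**Conclusion.** Wrong as written, as an internal contradiction of minor severity. Sections 9.2.2 and 9.4 set different denominators for the participant-level adherence proportion. The 9.4 set drops participants whom the 9.2.2 success definition scores. The 9.2.2 set takes in participants who never start cycle 2, without a scoring rule, and either scoring moves the rate away from adherence among those treated.

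Under the stated assumptions (36 enrolled, 4 non-starters split evenly, 80% true adherence) the reported rate is 75.6% or 81.1%. The enrolled-versus-transfused difference is a few points if 2 participants are untransfused, and probably small in practice.

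It would be going too far to call this a threat to the trial's feasibility conclusion. The outcomes are secondary, and the 70% criterion rests on haemoglobin measurements. What is at stake is whether the participant-level adherence rates, and their comparison between arms and sites, can be interpreted.

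**What to change.** In section 9.2.2, replace the enrolled denominator in both participant-level outcomes with: randomised participants who started that chemotherapy cycle under that strategy (for cycle 1, counted from randomisation), whether or not they were transfused.

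In section 9.4, state the same set for the proportion of participants. Keep the requirement of at least one transfusion only for measures whose unit is a transfusion or a pre-transfusion haemoglobin.

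Report the participants who never started cycle 2 separately, by sequence and by reason.

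The cost is two wording changes and one extra table row. No new data are needed, and neither the sample size nor the feasibility criterion changes.

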# 5. Treatment of Participants

#### 5.1 Introduction

This trial is a cross-over study of a control arm (threshold of ≤90 g/L) vs an intervention arm (threshold of ≤70 g/L). Participants will be randomised to be in one arm for their first cycle of treatment and the other arm for the second cycle of treatment. The arms are described in the sections below. The trial will compare two different policies for RBC transfusion, "restrictive" and "liberal". All recruited participants at a participating site should be transfused in accordance with the randomised transfusion policy for that cycle of treatment. Any transfusion required as part of the policy should be commenced within 24 hours of obtaining the haemoglobin result for inpatients and 72 hours for outpatients.

Prior to commencement of allocated transfusion policy in cycle 1, patients may receive red cell transfusions according to clinical need. This recognises the challenge of approaching and consenting patients at the time of new diagnosis and the importance of allowing patients and staff a short period of time to fully consider the trial. During this run-in period, red cell transfusion policies will be consistent with local guidelines, and typically at haemoglobin thresholds of 80g/L.

[figure not shown]
Allocation to either the restrictive or liberal policy will then apply from at or before Day 5 onwards in cycle 1. For cycle 2 chemotherapy treatment, participants will follow the alternative transfusion policy (ie if allocated to 'restrictive' arm for cycle 1, this would be the 'liberal' arm for cycle 2).

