# 5.2 Intervention Arm: Restrictive Transfusion Policy (RBCs transfused when haemoglobin ≤70g/L)

Following enrolment, the haemoglobin values of participants will be recorded according to routine clinical care. If the haemoglobin value is recorded as ≤70 g/L, red blood cells should be transfused at a dose of 1 unit at a time, with the aim of keeping the haemoglobin range between 71-80 g/L. The timing of repeat haemoglobin measurements should be decided by the attending haematologist. Further red blood cell transfusions should only be administered if the haemoglobin value decreases to a value of 70g/L or less (see figure 1). Any transfusion required as part of the policy should be administered within 24 hours of obtaining the haemoglobin result (up to 72 hours for outpatients). For participants with haemoglobin values significantly lower than the threshold (i.e. where one unit would not be expected to increase the haemoglobin level into the desired range) more than 1 unit at a time may be transfused.

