# 5.3 Control Arm: Liberal Transfusion Policy (RBCs transfused when haemoglobin ≤90g/L)

Following enrolment, the haemoglobin values of participants will be recorded according to routine clinical care. If the haemoglobin value is recorded as ≤90 g/L, red blood cells should be transfused at a dose of 1 unit with the aim of keeping the haemoglobin range between 91-100 g/L. The timing of repeat haemoglobin measurements should be decided by the attending haematologist. Further red blood cell transfusions should only be administered if the haemoglobin value decreases to a value of 90g/L or less (see figure 2). Any transfusion required as part of the policy should be administered within 24 hours of obtaining the haemoglobin result (or 72 hours for outpatients). For participants with haemoglobin values significantly lower than the threshold (i.e. where one unit would not be expected to increase the haemoglobin level into the desired range), more than 1 unit at a time may be transfused.

[figure not shown]

Figure 2: Control Arm: Liberal transfusion strategy

\*or 2 units for outpatients at clinician's discretion

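### Section 9.2.2 scores every transfusion against 24 hours while sections 5.1–5.3 give outpatients 72 hours, so outpatient transfusions given between those limits are permitted yet count as violations

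*Protocol*

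**What the plan says.** **Instructions to sites.** Protocol section 5.1 says that a transfusion required by the policy "should be commenced within 24 hours of obtaining the haemoglobin result for inpatients and 72 hours for outpatients". Section 5.2 repeats the outpatient allowance for the restrictive arm ("up to 72 hours for outpatients") and section 5.3 for the liberal arm ("or 72 hours for outpatients"). All three count from obtaining the result, and both arms act at or below the threshold (≤70 or ≤90 g/L).

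**Scoring.** The first adherence outcome in section 9.2.2 is the proportion of participants for whom the policy was followed throughout the cycle. It requires a timely transfusion every time, "when their haemoglobin dropped below the trigger level", and no transfusion above the trigger. It mentions a time frame but gives no number. The second outcome is the same with one violation allowed. The closing paragraph of 9.2.2 supplies the number: "Transfusions will only be viewed as having successfully followed the transfusion policy if they are given within the pre-defined time period of 24 hours". The same paragraph plans to follow adherence over time and to compare it between arms and between sites.

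**Outpatients are in scope.** Section 5.4 expects mainly inpatient stays but recognises that some participants will be treated as outpatients. Section 9.2.2 reports some transfusion outcomes by setting.

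**The concern.** This is a feasibility trial, and its hypothesis is that adherence to the two thresholds can be achieved. An adherence measure should record departures from what sites were told to do. Here the scoring rule is stricter than the instruction for one group of transfusions, so a site can follow section 5 exactly and still be recorded as non-adherent. The outcome requiring the policy to be followed every time is the most exposed, because a single permitted outpatient transfusion at, say, 48 hours turns a compliant participant into a failure. Sites with more outpatient care would look less adherent for that reason alone, and a change in outpatient care over the trial would look like a change in adherence.

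**Working it through.** **Step 1: the rules side by side.**

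| | Sections 5.1–5.3 | Section 9.2.2, closing paragraph |
|---|---|---|
| Inpatient limit | 24 h | 24 h |
| Outpatient limit | 72 h | 24 h (no exception stated) |
| Clock starts | when the result is obtained | when haemoglobin has dropped below the trigger |
| Boundary | ≤70 / ≤90 g/L | below the trigger |

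An outpatient transfusion within 24 hours passes both rules, and one after 72 hours fails both. Only those after 24 and up to 72 hours are scored differently. Section 9 gives no other figure for the time limit, so nothing there resolves the conflict. Section 5 also differs within itself on the event being timed: 5.1 has "commenced within 24 hours of obtaining the haemoglobin result for inpatients and 72 hours for outpatients", while 5.2 has "administered within 24 hours of obtaining the haemoglobin result (up to 72 hours for outpatients", and 5.3 uses the same verb as 5.2.

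**Step 2: which outcomes carry a time element.**

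- Policy always followed, and policy followed with one violation allowed (9.2.2): yes.
- Adherence over time, between arms and between sites (9.2.2, closing paragraph): yes, through the same rule.
- Proportions of transfusions correctly given, including the inpatient/outpatient split (9.2.2): no; defined by haemoglobin against the trigger.
- Primary adherence outcome (9.2.1) and the ≥70% criterion (9.4): no; both use pre-transfusion haemoglobin only.

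**Step 3: share of transfusions mis-scored.** The Protocol gives no figure to reproduce. Let q be the outpatient share of transfusions and f the fraction of outpatient transfusions given after 24 and up to 72 hours. The mis-scored share is q × f. Both inputs are assumptions: q from 5% to 30%, f from 10% to 75%.

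- Low: 0.05 × 0.10 = 0.005, or 0.5 percentage points
- Middle: 0.20 × 0.50 = 0.10, or 10 points
- High: 0.30 × 0.75 = 0.225, or 22.5 points

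**Step 4: participant level.** Take a participant who complies with section 5 throughout and has k outpatient transfusions in a cycle, each with independent chance f of falling in the window.

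- P(scored not followed) = 1 − (1 − f)^k
- P(scored not followed, one violation allowed) = 1 − (1 − f)^k − k f (1 − f)^(k−1)

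| k | Always followed: f = 25% | f = 50% | One violation allowed: f = 25% | f = 50% |
|---|---|---|---|---|
| 1 | 25% | 50% | 0% | 0% |
| 2 | 44% | 75% | 6% | 25% |
| 3 | 58% | 88% | 16% | 50% |

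For example, k = 2 and f = 25% gives 1 − 0.75² = 0.4375 for the first outcome, and 0.25² = 0.0625 with one violation allowed.

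**Step 5: the boundary.** A transfusion at exactly 70 or 90 g/L is not above the trigger, so it is no violation under either wording. The one gap is a value exactly at the trigger that is not transfused. Section 5 calls for a transfusion, but the participant-level definition in 9.2.2 does not register the omission. Other bullets in 9.2.2 already use ≤ and >.

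**The case against.** The strongest reply is that the reach is narrow. Section 5.4 describes mainly inpatient stays, so outpatient transfusions may be few; at the low end of step 3 the effect is negligible. That stands, and the upper figures should not be read as expected values.

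A reader might infer that the feasibility decision is at risk. It is not: the primary adherence outcome and the ≥70% criterion have no time element. A reader might also infer that the inpatient/outpatient comparison is an artefact of the 24-hour rule. The text does not support that either, because that outcome counts transfusions that were correct by haemoglobin trigger. For the same reason, the figures in step 3 attach to none of the listed transfusion-level proportions. They bear only on the less closely specified adherence rates in the closing paragraph of 9.2.2.

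For the comparison between arms, participants are meant to contribute a cycle to each policy, and the Protocol gives no reason to expect the outpatient share to differ by arm. Section 6.2.6.1 says that its look at how site systems affect adherence is not powered to identify significant differences. Both points limit the consequences without removing the conflict.

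The differences in clock start and boundary are minor. A fall is known only through a measured result, and the boundary matters only in the case described in step 5.

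Finally, it may be said that the SAP settles the matter. It may, but 9.2.2 does not leave the limit open: it states one, and that limit conflicts with section 5.

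**Conclusion.** The contradiction stands. As written, 9.2.2 scores outpatient transfusions given after 24 and up to 72 hours as violations although sections 5.1–5.3 permit them. The damage is confined to two participant-level secondary outcomes and the adherence comparisons over time, between arms and between sites.

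The size cannot be fixed from the Protocol, because neither q nor f is stated. The range of 0.5 to 22.5 percentage points is only as good as the assumed inputs. The participant-level probabilities apply only to participants who have outpatient transfusions, and they assume independence between those transfusions. Allowing one violation softens the effect but does not remove it once a participant has two or more outpatient transfusions in a cycle. This should be corrected, but it does not threaten the main conclusion of the trial.

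**What to change.** Reconcile sections 5.1, 5.2, 5.3 and 9.2.2 so that each transfusion is scored against the same window for its setting, the same clock start and the same timed event (start or administration) that sites are instructed to follow. Which window is right is a clinical matter for the sponsor and is not judged here; what matters is that the instruction and the score agree. As a wording correction, use in the participant-level definition and the closing paragraph of 9.2.2 the ≤/> boundary that the other bullets already use.

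The cost is about two sentences in 9.2.2, alignment of the wording in section 5, and a check of the matching SAP derivation. Section 6.2.5 already records haemoglobin dates and times, and 9.2.2 already needs inpatient or outpatient status. The existing 24-hour rule needs the time of transfusion in any case, so no new data item is required.
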